5.4.2 Follow-up of Unresolved Adverse Events

Any AEs that are unresolved at the subject’s last visit in the study are followed up by the investigator for as long as medically indicated, but without further recording in the eCRF. MedImmune retains the right to request additional information for any subject with ongoing AE(s)/SAE(s) at the end of the study, if judged necessary. Updates regarding SAEs that were ongoing at the time of the subject’s completion of study participation should be submitted to the study representative using a paper SAE follow-up form.

5.5 Reporting of Serious Adverse Events

All SAEs have to be reported, whether or not considered casually related to the investigational product, or to the study procedure(s). All SAEs will be recorded in the eCRF.

If any SAE occurs during the course of the study, the investigator or other site personnel will inform the appropriate sponsor representative(s) within 1 day; ie, immediately but no later than 24 hours of when he or she becomes aware of the event.

The designated sponsor representative works with the investigator to ensure that all the necessary information is provided to the sponsor patient safety data entry site within 1 calendar day of initial receipt for fatal and life-threatening events and within 5 calendar days of initial receipt for all other SAEs.

For fatal or life-threatening AEs where important or relevant information is missing, active follow-up is undertaken immediately. Investigators or other site personnel will inform sponsor representatives of any follow-up information on a previously reported SAE within

1 calendar day; ie, immediately but no later than 24 hours of when he or she becomes aware of the event.

Once the investigator or other site personnel indicate an AE is serious in the electronic data capture (EDC) system, an automated email alert is sent to inform the designated sponsor representative(s).

If the EDC system is not available, then the investigator or other study site personnel report the SAE to the appropriate sponsor representative by telephone. The sponsor representative will advise the investigator/study site personnel how to proceed.

5.6 Other Events Requiring Immediate Reporting

5.6.1 Overdose

An overdose in this study is defined as a subject receiving a dose of investigational product that is greater than the dose that was intended to be given:

- An overdose with associated AEs is recorded as the AE diagnosis/symptoms on the relevant AE modules in the eCRF and on the Overdose eCRF module.
- An overdose without associated symptoms is only reported on the Overdose eCRF module.

If an overdose with a MedImmune investigational product occurs during the course of the study, then the investigator or other site personnel inform appropriate sponsor representatives immediately, or no later than 24 hours after becoming aware of the event.

The designated sponsor representative works with the investigator to ensure that all relevant information is provided to the sponsor's patient safety data entry site.

For overdoses associated with an SAE, the standard reporting timelines apply; see Section 5.5. For other overdoses, reporting must occur within 30 days.

5.6.2 Hepatic Function Abnormality

Cases where a subject shows elevations in liver biochemistry may require further evaluation and occurrences of AST or ALT $\geq 3 \times$ ULN together with total bilirubin $\geq 2 \times$ ULN may need to be reported as SAEs. Refer to Section 10.5 for further instruction on cases of increases in liver biochemistry and evaluation of Hy's law.

5.6.3 Pregnancy

All pregnancies and outcomes of pregnancy should be reported to the sponsor.

5.6.3.1 Maternal Exposure

Women of childbearing potential in this study who are sexually active with a nonsterilized male partner are required to use 1 form of contraception as described in the inclusion criteria. Pregnancy should be avoided for at least 28 days after receiving investigational product or until the subject completes participation in the study, whichever is longer. If a subject becomes pregnant during the course of the study, investigational product should be discontinued immediately.

Pregnancy itself is not regarded as an AE unless there is a suspicion that the investigational product under study may have interfered with the effectiveness of a contraceptive medication. Congenital abnormalities/birth defects and spontaneous miscarriages should be reported and handled as SAEs. Elective abortions without complications should not be handled as AEs. The outcome of all pregnancies (spontaneous miscarriage, elective termination, ectopic pregnancy, normal birth, or congenital abnormality) should be followed up and documented even if the subject was discontinued from the study.

If any pregnancy occurs in the course of the study, then the investigator or other site personnel inform the appropriate sponsor representatives within 1 day; ie, immediately but no later than 24 hours of when he or she becomes aware of it.

The designated sponsor representative works with the investigator to ensure that all relevant information is provided within 1 or 5 calendar days for SAEs (Section 5.5) and within 30 days for all other pregnancies.

The same timelines apply when outcome information is available.

Any subject who becomes pregnant during the course of the study will be followed so that pregnancy outcome can be determined and reported to the sponsor and the regulatory authorities.

6 STUDY AND DATA MANAGEMENT

6.1 Training of Study Site Personnel

Before the first subject is entered into the study, a MedImmune representative will review and discuss the requirements of the Clinical Study Protocol and related documents with the

investigational staff and also train them in any study-specific procedures and system(s) utilised.

The principal investigator will ensure that appropriate training relevant to the study is given to all of these staff, and that any new information relevant to the performance of this study is forwarded to the staff involved.

The principal investigator will maintain a record of all individuals involved in the study (medical, nursing, and other staff).

6.2 Monitoring of the Study

During the study, a MedImmune representative will have regular contacts with the study site, including visits to:

- Provide information and support to the investigator(s)
- Confirm that facilities remain acceptable
- Confirm that the investigational team is adhering to the protocol, that data are being accurately and timely recorded in the eCRFs, that biological samples are handled in accordance with the Laboratory Manual, and that study drug accountability checks are being performed
- Perform source data verification (a comparison of the data in the eCRFs with the subject's medical records at the hospital or practice, and other records relevant to the study) including verification of informed consent of participating subjects. This will require direct access to all original records for each subject (eg, clinic charts).
- Ensure withdrawal of informed consent to the use of the subject's biological samples is reported and biological samples are identified and disposed of/destroyed accordingly, and the action is documented, and reported to the subject.

The MedImmune representative will be available between visits if the investigator(s) or other staff at the centre needs information and advice about the study conduct.

6.2.1 Source Data

Refer to the Clinical Study Agreement for location of source data.

6.2.2 Study Agreements

The principal investigator at each centre should comply with all the terms, conditions, and obligations of the Clinical Study Agreement, or equivalent, for this study. In the event of any inconsistency between this Clinical Study Protocol and the Clinical Study Agreement, the

terms of Clinical Study Protocol shall prevail with respect to the conduct of the study and the treatment of subjects and in all other respects, not relating to study conduct or treatment of subjects, the terms of the Clinical Study Agreement shall prevail.

Agreements between MedImmune and the principal investigator must be in place before any study-related procedures can take place, or subjects are enrolled.

6.2.3 Archiving of Study Documents

The investigator follows the principles outlined in the Clinical Study Agreement.

6.3 Study Timetable and End of Study

An individual subject will be considered to have completed the study if the subject was followed through the last protocol-specified visit/assessment, regardless of the number of doses of investigational product that was received.

Subjects will be considered not to have completed the study if consent was withdrawn or the subject was lost to follow-up (Sections 4.1.5 and 4.1.6).

The end of the study (“study completion”) is defined as the date of the last protocol-specified visit/assessment for the last subject in the study.

6.4 Data Management

Data management will be performed by MedImmune Data Management staff according to the Data Management Plan.

A web based data capture system will be used for data collection and query handling. The investigator will ensure that data are recorded on the eCRFs as specified in the study protocol and in accordance with the instructions provided.

The investigator ensures the accuracy, completeness, and timeliness of the data recorded and of the provision of answers to data queries according to the Clinical Study Agreement. The investigator will sign the completed eCRFs. A copy of the completed eCRFs will be archived at the study site.

6.5 Medical Monitor Coverage

Each subject will be provided with contact information for the principal investigator. In addition, each subject will receive a toll-free number intended to provide the subject’s physician access to a medical monitor 24 hours a day, 7 days a week in the event of an

emergent situation where the subject's health is deemed to be at risk. In this situation, when a subject presents to a medical facility where the treating physician or health care provider requires access to a physician who has knowledge of the investigational product and the clinical study protocol and the principal investigator is not available, the treating physician or health care provider can contact a medical monitor through this system, which is managed by a third party vendor.

7 ETHICAL AND REGULATORY REQUIREMENTS

7.1 Subject Data Protection

Each subject will be assigned a SID to ensure that personally identifiable information is kept separate from the study data. Subject data that are relevant to the trial, eg, demographic information, physical or mental health condition, diagnosis, comorbidities, laboratory test results, etc will only be collected with the subject's informed consent. The informed consent form (ICF) will incorporate (or, in some cases, be accompanied by a separate document incorporating) wording that describes how subject data will be collected, used, and distributed in compliance with relevant data protection and privacy legislation.

[REDACTED]

7.2 Ethics and Regulatory Review

The IEC responsible for each site must review and approve the final study protocol, including the final version of the ICF and any other written information and/or materials to be provided to the subjects. The IEC must also approve all advertising used to recruit subjects for the study. The investigator or representative is responsible for submitting these documents to the applicable IEC and distributing them to the study site staff.

The opinion of the IEC should be given in writing. The investigator should submit the written approval to MedImmune before enrolment of any subject into the study.

The IEC should approve all advertising used to recruit subjects for the study.

MedImmune should approve any modifications to the ICF that are needed to meet local requirements.

If required by local regulations, the protocol should be re-approved by the IEC annually.

Before the study is initiated, MedImmune will ensure that the national regulatory authority in each country has been notified and their approval has been obtained, as required.

MedImmune will provide safety updates/reports according to local requirements, including suspected unexpected serious adverse reactions where relevant, to regulatory authorities, IEC, and principal investigators.

Each principal investigator is responsible for providing the IEC with reports of any serious and unexpected adverse drug reactions from any other study conducted with the investigational product. MedImmune will provide this information to the principal investigator so that he/she can meet these reporting requirements.

7.3 Informed Consent

Informed consent of each subject will be obtained through a written and verbal explanation process that addresses all elements required by ICH/GCP. MedImmune will develop a core ICF for use by all investigators in the clinical study. MedImmune must approve any modifications to the ICF that are needed to meet local requirements.

The principal investigator(s) at each centre will:

- Ensure each subject is given full and adequate oral and written information about the nature, purpose, possible risk, and benefit of the study
- Ensure each subject is notified that they are free to discontinue from the study at any time
- Ensure that each subject is given the opportunity to ask questions and allowed time to consider the information provided
- Ensure each subject provides signed and dated informed consent before conducting any procedure specifically for the study
- Ensure the original, signed ICF(s) is/are stored in the Investigator's Study File
- Ensure a copy of the signed ICF is given to the subject
- Ensure that any incentives for subjects who participate in the study as well as any provisions for subjects harmed as a consequence of study participation are described in the ICF that is approved by an IEC

7.4 Changes to the Protocol and Informed Consent Form

Study procedures will not be changed without the mutual agreement of the principal investigator and MedImmune.

Substantial changes must be documented in a study protocol amendment. MedImmune will distribute amended versions of the protocol to the principal investigator(s). Before

implementation, amended protocols must be approved by relevant IEC (Section 7.2) and according to local requirements, the national regulatory authority approval. The IEC must also approve revisions to the ICF, advertising, and any other written information and/or materials resulting from the change to the protocol.

If local regulations require, any administrative change will be communicated to or approved by each IEC.

7.5 Audits and Inspections

Authorized representatives of MedImmune, a regulatory authority, or an IEC may perform audits or inspections at the centre, including source data verification. The purpose of an audit or inspection is to systematically and independently examine all study-related activities and documents, to determine whether these activities were conducted, and data were recorded, analysed, and accurately reported according to the protocol, GCP, guidelines of the ICH, and any applicable regulatory requirements. The investigator will contact MedImmune immediately if contacted by a regulatory agency about an inspection at the site.

9 CHANGES TO THE PROTOCOL

9.1 Protocol Amendment 2, 17Oct2017

Text revisions resulting from this amendment are incorporated in the body of Protocol Amendment 2. Key changes to the protocol are summarized in the table below.

Table 9.1-1 Summary of Revisions to the Protocol

Key Details of Amendment	Reason for Amendment
Amendment 2 / 17Oct2017	
Table 4.2.2-1 (Schedule of Treatment Period Study Procedures: Cohort 1)	Footnote “u” amended to clarify that a new CGM can be applied at any time on Day 36, and that the CGM sensor should be removed after 0800 hours on Day 50.
Table 4.2.1-1 (Schedule of Screening Procedures), Table 4.2.2-1 (Schedule of Treatment Period Study Procedures: Cohort 1), Table 4.2.2-2 (Schedule of Treatment Period Study Procedures: Cohort 2), Table 4.2.3-1 (Schedule of Follow-up Procedures) and Section 4.3.2.4 (Vital Signs)	Table footnotes and text in Section 4.3.2.4 amended to clarify that vital signs can be taken after a subject has rested for 10 minutes in a seated or supine position.
Table 4.2.2-1 (Schedule of Treatment Period Study Procedures: Cohort 1) and Table 4.2.2-2 (Schedule of Treatment Period Study Procedures: Cohort 2)	Text added to clarify that the additional blood test for safety should be taken at any time between Day -7 and Day -3, if required.
Table 4.2.2-2 (Schedule of Treatment Period Study Procedures: Cohort 2)	The instruction to fast on the night of Day 7 was removed from footnote “i” to correct a previous oversight.
Table 4.2.3-1 (Schedule of Follow-up Procedures)	Text referring to a postdose sample in footnote “b” was removed to correct a previous oversight.
Section 4.2.3.1 (Early Discontinuation Visit or Unscheduled Study Visit)	Text was edited to allow flexibility around the order of assessments based on site feedback.
Section 4.3.1.1 (Mixed-meal Tolerance Tests)	The timeframe to consume a standardised liquid meal was changed from “15 minutes” to “5 minutes” to correct a previous oversight.
Section 5.4.1 (Time Period for Collection of Adverse Events)	The timeframe of SAE collection was updated for consistency with internal MedImmune processes.
Section 5.6.3.1 (Maternal Exposure)	Text was amended to state that women of childbearing potential in this study who are sexually active with a nonsterilized male partner are required to use 1 form of contraception. This change was made to correct a previous oversight and for consistency with the inclusion criteria.
Section 10.2 (Appendix 2-Contraception Guidance)	Text in bold added to the definition of postmenopausal to correct a previous oversight: “defined as at least 1 year since last menses and/or having an elevated follicle-stimulating hormone level in the postmenopausal range in previous laboratory test results.”

9.2 Protocol Amendment 1, 25Jul2017

Text revisions resulting from this amendment are incorporated in the body of Protocol Amendment 1. Key changes to the protocol are summarized in the table below.

Table 9.2-1 Summary of Revisions to the Protocol

Key Details of Amendment	Reason for Amendment
Amendment 1 / 25Jul2017	
Synopsis	Changes made to be consistent with the body of the protocol
[REDACTED]	[REDACTED]
Section 3.1.1 Overview, Section 4.3.3 Clinical Laboratory Tests	Subjects will undergo safety blood tests at any time from Day -7 to Day -3 if the screening visit is more than 7 days before Day 1 at the request of the ethics committee.
Section 3.1.4.3 Hyperglycemia	Additional guidance around management of hyperglycemia was added in response to feedback from the ethics committee.
Section 4.1.3 Exclusion criteria	Additional criterion #19 was added at the request of the ethics committee to exclude subjects with a history of acute or chronic pancreatitis or other diseases of the pancreas. Definition of hypertension was modified based on feedback from the ethics committee.
Section 4.1.3 Exclusion criteria, Table 4.2.1-1 Schedule of Screening Procedures, Table 4.2.2-1 Schedule of Treatment Period Study Procedures: Cohort 1, Section 4.3.3 Clinical Laboratory Tests	Additional criteria for alcohol abuse or excessive alcohol intake were added to the protocol in response to a request from the German Federal Institute for Drugs and Medical Devices (Bundesinstitut für Arzneimittel und Medizinprodukte [BfArM]).
Section 4.1.7 Replacement of Subjects	Stipulation that a maximum number of five subjects may be replaced in each cohort in response to a request from the BfArM.
Section 4.7.2 Prohibited Concomitant Medications	Additional restrictions around initiation of new medications to control blood glucose levels were included in response to a request from the BfArM.
Table 4.2.2-1 Schedule of Treatment Period Study Procedures: Cohort 1	Table footnote corrected to state that for MMTT Type C the subject should be fasted from 1400 hours. Correction of typographical error. Screening blood samples were added at the request of the ethics committee.
Table 4.2.2-2 Schedule of Treatment Period Study Procedures: Cohort 2	The table cells were corrected so that randomization occurs on Day-1 to Day 1 consistent with other

Table 9.2-1 Summary of Revisions to the Protocol

Key Details of Amendment	Reason for Amendment
	
sections of the protocol. The uptitration schedule was also corrected from Day 14 to Day 15.
 
Footnote describing timings for MMTT Type A and Type B was corrected to be consistent with other sections of the protocol.
 
Correction of typographical errors.
 
Screening blood samples were added at the request of the ethics committee.

Section 4.3.1.1 Mixed-meal Tolerance Tests	
Text describing the timing of consumption of Ensure Plus (within 15 minutes) was clarified to be consistent with other sections of the protocol.
 
Correction of typographical error.

Section 4.3.2.4 Vital Signs	
Corrected to state that vital signs measurements will be taken with the subject in a seated position.
 
Correction of typographical error.

Table 4.5.1.3-1 MEDI0382 and Placebo Dose Preparation	
The number of units for the 300 µg dose was corrected to 15.
 
The example given for units calculation has been changed to be consistent with the table for clarity.
 
Correction of typographical error.

Section 4.5.1.4 Treatment Administration	
Clarification that investigational product will be administered by SC injection in the lower abdomen utilising either a 0.3-mL or a 1-mL insulin syringe according to the dose level.
 
Correction of typographical error.

Section 4.3.8 Blood Volumes	
Total blood volumes to be drawn in both cohorts have been reduced.

Section 4.7.2 Prohibited Concomitant Medication	
Additional guidance around the allowed use of concomitant medications to control blood glucose were added at the request of the ethics committee.

Section 4.8.2 Sample Size and Power Calculations	
The overall power for both primary endpoints was added at the request of the ethics committee.

Table 10.2-1 Highly Effective Methods of Contraception	
The table has been modified to remove reference to oral contraceptives at the request of the ethics committee.

10.2 Appendix 2 – Contraception Guidance

For females of childbearing potential:

- Females of childbearing potential are defined as those who are not surgically sterile (ie, surgical sterilisation includes bilateral tubal ligation, bilateral oophorectomy, or complete hysterectomy) or those who are not postmenopausal (defined as at least 1 year since last menses and/or having an elevated follicle-stimulating hormone level in the postmenopausal range in previous laboratory test results).

A highly effective method of contraception is defined as one that results in a low failure rate (ie, less than 1% per year) when used consistently and correctly. The acceptable methods of contraception are described in [Table 10.2-1](#).

Female subjects must refrain from egg cell donation while in study and for 28 days after the final dose of investigational product.

Table 10.2-1 Highly Effective Methods of Contraception

• Tubal occlusion• Copper T intrauterine device• Levonorgestrel-releasing intrauterine system (eg, Mirena[®])• Medroxyprogesterone injections (eg, Depo-Provera[®])• Etonogestrel implants (eg, Implanon[®], Norplan[®])• Norelgestromin/ethinyl estradiol transdermal system• Intravaginal device (eg, NuvaRing[®])

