4.1.2 Inclusion Criteria

Subjects must meet all of the following criteria:

1. Male and female subjects aged ≥ 18 years at screening
2. Provision of signed and dated written informed consent (██████████ nongenetic research) prior to any study specific procedures
3. BMI between 27 and 40 kg/m² (inclusive) at screening
4. HbA1c range of 6.5% to 8.5% (inclusive) at screening*
5. Diagnosed with T2DM with glucose control managed with metformin monotherapy where no significant dose change (increase or decrease ≥ 500 mg/day) has occurred in the 3 months prior to screening
6. Subjects prescribed oral dual therapy with a dipeptidyl peptidase-4 inhibitor, sulphonylurea, glitinide, or a sodium-glucose co-transporter 2 inhibitor in addition to metformin at screening may be eligible to enter the study following a 4-week washout period
7. Female subjects of childbearing potential must have a negative pregnancy test at screening and randomisation, and must not be lactating
8. Females of childbearing potential who are sexually active with a nonsterilised male partner must use at least one highly effective method of contraception (see Section 10.2 for definition of females of childbearing potential and for a description of highly effective methods of contraception) from screening and must agree to continue using such precautions through to the end of the study. It is strongly recommended for the male partner of a female subject to also use male condom plus spermicide throughout this period. Cessation of contraception after this point should be discussed with a responsible physician. Periodic abstinence, the rhythm method, and the withdrawal method are not acceptable methods of contraception.

*Note: Subjects may be retested for the HbA1c entry criterion only once.

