4.2 Schedule of Study Procedures

4.2.1 Enrollment/Screening Period

Table 4.2.1-1 shows all procedures to be conducted at the screening visit. Assessments should be performed in the order shown in the table.

Whenever vital signs, 12-lead ECGs, and blood draws are scheduled for the same nominal time, the assessments should occur in the following order: 12-lead ECG, vital signs, and then blood draws. The timing of the first 2 assessments should be such that it allows the blood draw (eg, MMTT blood sample) to occur at the exact nominal time.

Table 4.2.1-1 Schedule of Screening Procedures

Study Period	Screening
Visit Number	V1
Procedure/Study Day	Day -60 to Day -2
Written informed consent/assignment of SID number	X
[REDACTED]	■
[REDACTED]	■

Table 4.2.1-1 Schedule of Screening Procedures

Study Period	Screening
Visit Number	V1
Procedure/Study Day	Day -60 to Day -2
Medical history, including smoking and alcohol history	X
Physical examination (full) including structured neurological examination ^a	X
Verify eligibility criteria	X
Weight, height, and BMI calculation	X
Demographics	X
12-lead ECG ^b	X
Vital signs (BP ^c , heart rate, body temperature, RR)	X
Collect blood for:	
LFTs, CR, and eGFR calculation only	X
Haematology (FBC)	X
HbA1c	X
Calcitonin	X
HIV-1 and -2 antibodies; hepatitis B and C serology	X
Collect urine for:	
Urinalysis	X
Drug and alcohol screen	X
Urine or serum pregnancy test if applicable	X
CGM device demonstration ^d	X
SC injection self-administration training ^e	X
Concomitant medications	X

BMI = body mass index; BP = blood pressure; CGM = continuous glucose monitoring; CR = creatinine; ECG = electrocardiogram; eGFR = estimated glomerular filtration rate; FBC = full blood count; HbA1c = glycated haemoglobin; HIV = human immunodeficiency virus; LFTs = liver function tests (albumin; alanine transaminase [ALT], aspartate transaminase [AST], alkaline phosphatase [ALP], and total bilirubin); RR = respiration rate; SC = subcutaneous; SID = subject identification; V = visit

^a examination is required.

^b A single digital ECG recording should be performed after the subject has rested in the supine position for 10 minutes.

^c Blood pressure should be measured once at heart level in the nondominant arm where possible, after the subject has rested in either a seated or supine position for at least 10 minutes.

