Note: Whenever vital signs, ECGs, and blood draws are scheduled for the same nominal time, the ECG should occur first, then vital signs, and blood draws should occur last. The timing of the ECGs and/or vital signs should be such that it allows the blood draw (eg, for PK and PD) to occur as close as possible to the scheduled time. Ten minutes of supine rest should precede these assessments.

- a The eligibility check should be based on all clinical measurements and blood tests taken during the screening visit (V1) with the exception of eGFR, liver function tests, blood pressure, urinary illicit drug, alcohol and pregnancy tests, which should be rechecked on Day -2. A targeted physical examination and repeat medical history should also be undertaken to ensure the subject is well enough to commence dosing.
- b The diet of subjects should not be restricted in any way during the study (including during inpatient stay) unless fasting or a standardised meal is specified.
- c Subjects who prefer to attend for daily visits during the first week will be discharged home on Day 1 after all assessments are complete. (X) indicates that subjects can be inpatients or outpatients at these visits.
- d A serum or urine pregnancy test should be conducted on any female subject of childbearing potential as detailed in the schedule. Pregnancy tests do not need to be conducted in women who are surgically sterile (ie, bilateral tubal ligation, bilateral oophorectomy, or complete hysterectomy) or are postmenopausal (defined as at least 1 year since last menses and having an elevated follicle stimulating hormone laboratory value which is in the postmenopausal range in previous laboratory test results).
- e Vital Signs Schedule (blood pressure, heart rate, respiratory rate, and temperature): on days where ABPM is due to be checked a predose set of vital signs should be performed prior to application of the ABPM cuff. Blood pressure should be measured once at heart level in the nondominant arm where possible, opposite to the arm where the CGM device is applied, after the subject has rested in either a seated or supine position for at least 10 minutes. For time points where ECG recording precedes vital sign measurement, the 10-minute rest in the supine position prior to the ECG suffices for the rest prior to vital sign measurement.
 - o Day -2; vital signs to be taken prior to fitting the ABPM device; postural (standing and supine) blood pressures should be performed at this time.

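### On its workable reading, Section 10.2's *and/or* would release a non-sterilised woman with menses in the past year from the contraception rule on an old FSH result alone, although footnote d of both treatment schedules does not count her as postmenopausal

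*Protocol*

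**What the plan says.** Inclusion criterion 8 (Protocol Section 4.1.2) requires a highly effective contraceptive method from females of childbearing potential who are sexually active with a male partner who has not been sterilised. For the definition it sends the reader to the appendix: "see Section 10.2 for definition of females of childbearing potential and for a description of highly effective methods of contraception". The obligation runs "from screening and must agree to continue using such precautions through to the end of the study". Section 5.6.3.1 (Maternal Exposure) adds no definition of its own; such women are "required to use 1 form of contraception as described in the inclusion criteria".

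Section 10.2 (Appendix 2) defines childbearing potential by two limbs joined by *or*: not surgically sterile, or not postmenopausal. Postmenopausal means a year or more without menses "and/or having an elevated follicle-stimulating hormone level in the postmenopausal range in previous laboratory test results".

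Footnote d of Tables 4.2.2-1 and 4.2.2-2 (Section 4.2.2) waives pregnancy testing for women who are surgically sterile or postmenopausal. It uses a stricter definition of the latter: "defined as at least 1 year since last menses and having an elevated follicle stimulating hormone laboratory value", the value again being in the postmenopausal range in earlier results.

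On testing itself, footnote a of both tables lists "alcohol and pregnancy tests, which should be rechecked on Day -2". The screening schedule (Table 4.2.1-1) has "Urine or serum pregnancy test if applicable". The final-visit schedule (Table 4.2.3-1) lists a pregnancy test without that qualifier.

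**The concern.** Two current parts of the protocol define the same status differently, and the looser one governs prevention. With *and/or*, either condition is enough, so a single earlier FSH value in the postmenopausal range makes a woman postmenopausal under Section 10.2 even if she has menstruated recently. Section 10.2 sets no age limit on that result and asks for no repeat. No FSH test appears in the screening schedule or the laboratory panels of Section 4.3.3, so the value would not be rechecked.

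What is at stake is subject safety. Section 5.6.3.1 states the aim: "Pregnancy should be avoided for at least 28 days after receiving investigational product", or until participation is complete if that is later. Contraception is the protocol's preventive means to that end. Scheduled tests and mandatory discontinuation on pregnancy (Sections 4.1.6 and 5.6.3.1) act only after conception.

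**Working it through.** The protocol gives no figure to reproduce. The check sets the definitions side by side and then counts days.

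**Definitions.** Take a woman who is not surgically sterile. Let M = a year or more since last menses and F = FSH in the postmenopausal range in earlier results.

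| M | F | Postmenopausal, 10.2 now (M or F) | Postmenopausal, footnote d (M and F) | Postmenopausal, 10.2 as proposed (M) |
|---|---|---|---|---|
| yes | yes | yes | yes | yes |
| yes | no | yes | no | yes |
| no | yes | yes | no | no |
| no | no | no | no | no |
| Total yes | | 3 of 4 | 1 of 4 | 2 of 4 |

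Section 10.2 and footnote d now disagree in 2 of 4 combinations (rows 2 and 3). Row 3, recent menses with a raised FSH, is the one of concern. In row 2 the woman has had no menses for a year or more, and footnote d is merely the more cautious text. Under the proposed wording the disagreement falls to 1 of 4 (row 2). If Section 10.2 copied footnote d's *and*, it would fall to 0 of 4.

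**Which reading of the two limbs.** Taken literally, the *or* makes every non-sterilised woman of childbearing potential whatever her menopausal status, and exempts only a woman who is both sterilised and postmenopausal. The postmenopausal limb would then have no effect for any non-sterilised woman. Footnote d treats sterility and menopause as alternative exemptions. The workable reading is therefore neither sterile nor postmenopausal, and row 3 is exempt only on that reading.

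**Duration.**
- First dose: Day 1. Last dose: Day 49 (Section 3.1.2).
- Final visit: 28 days after last dose, plus or minus 3 (Table 4.2.3-1), so 49 + 28 = Day 77, range Day 74 to Day 80.
- First dose to final visit: Day 1 to Day 77 = 77 days, plus or minus 3.
- Screening is between Day -60 and Day -2 (Table 4.2.1-1). Criterion 8 starts there, which adds 2 to 60 days before any investigational product is given.

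**Testing for the row 3 woman.** The waiver in footnote d does not cover her, because it needs both M and F. But footnote d opens by limiting testing to female subjects of childbearing potential, and criterion 7 (negative tests at screening and randomisation) uses the same term. If that term carries its Section 10.2 meaning, she is outside both. Footnote a's Day -2 recheck and the unqualified final-visit test point the other way. The text does not settle it.

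**The case against.** The strongest reply is that the gap may not exist. On the literal *or*, a non-sterilised woman needs contraception regardless of FSH. That stands as far as it goes: an unconditional statement that the protocol exempts her is a stronger reading that the documents do not support. It does not dispose of the point, because the literal reading empties the postmenopausal limb for exactly the women it is meant to classify and conflicts with footnote d.

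Second, the wording is deliberate. The Amendment 2 log (Section 9.1) records *and/or* in Section 10.2 as correcting an oversight. A reader might infer a drafting slip; the log rules that out, and log and current text agree. The discrepancy is with footnote d, which is also current. The log lists other changes to both schedule tables but none to that definition.

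Third, the consequence is easily overstated. A reader might count the whole criterion 8 period, up to 60 + 77 = 137 days, as time at risk. Up to 60 of those days precede any product, so the relevant figure is about 77. Even that is the period over which the protocol wants pregnancy avoided, not the time drug is present: the half-life in Section 3.2.1 is about 8 to 13 hours, and five half-lives at the upper value are 5 × 13 = 65 hours. The documents also give no information on how likely conception is in such a woman.

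Fourth, she may still be tested, and pregnancy stops dosing. That limits the harm. But neither the inference that she is certainly tested nor that she is certainly untested is supported, and testing does not prevent pregnancy.

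**Conclusion.** The point holds conditionally and is minor. On the workable reading of Section 10.2, a non-sterilised woman with menses in the past year and an earlier FSH in the postmenopausal range falls outside the contraception rule from first dose to her final visit, about 77 days (plus or minus 3), plus any screening time. Footnote d does not regard her as postmenopausal.

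This rests on three assumptions: the neither/nor reading; that criterion 8's end of study means the individual's final visit (Section 6.3 defines study completion by the last subject's last visit, which would be later for most subjects); and that she would otherwise meet criterion 8's condition on sexual activity and partner. The counts are of definitions and days, not of subjects; the number of women affected cannot be derived from the documents. A reader might infer some effect on the trial's results. There is none: no endpoint, estimate, sample size or error rate changes.

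**What to change.** Reword the definition in Section 10.2 only, for example: *Females of childbearing potential are those who are neither surgically sterile nor postmenopausal; postmenopausal requires at least 1 year since last menses, and an FSH in the postmenopausal range in previous results is not sufficient on its own.* This also removes the ambiguity of the two limbs joined by *or*. Leave footnote d of both schedules unchanged, so that no pregnancy test is removed.

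The cost is one reworded definition at the next amendment, with no FSH test added. Women with recent menses and a raised FSH on record would need contraception if criterion 8's condition on sexual activity and partner applies to them, and would come clearly within the pregnancy-testing rules. Row 2 would still differ between the two texts: no contraception required, but the testing waiver not met.

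The alternative is to put footnote d's *and* into Section 10.2. That aligns all four combinations, but it would demand contraception from women a year or more past their last menses simply because no FSH result is on file. The proposed wording keeps amenorrhoea alone as sufficient, which the current *and/or* already allows.
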